#### **4.3 Dose Selection**

A dose of bempedoic acid 180 mg once per day was selected based on approved doses by the US FDA ([Nexletol](#)) and the European Medicines Agency ([Nilemdo](#)). The dose for bempedoic acid/ezetimibe FCDP (bempedoic acid 180 mg/ezetimibe 10 mg) was selected based on approved doses by the US FDA ([Nexlizet](#)) and the European Medicines Agency ([Nustendi](#)). For additional information please refer to the most recent [IB](#), the [USPIs](#) for [Nexletol](#) and [Nexlizet](#) and the [SmPCs](#) for [Nilemdo](#) and [Nustendi](#).

Subjects enrolled in the study will be dosed for 6 consecutive days in order to reach steady-state concentrations of bempedoic acid or bempedoic acid and ezetimibe in plasma. Steady-state concentrations in plasma are expected after 5 to 7 days of repeat dosing as estimates of elimination half-life of bempedoic acid and ezetimibe are each approximately 24 hours. A once daily dosing regimen for 6 days will achieve plasma concentrations that are approximately 98% of steady-state levels. Six days of repeat dosing have been selected to ensure subjects are at steady-state plasma concentrations of bempedoic acid or bempedoic acid and ezetimibe for pharmacokinetic (PK) assessments.

#### **4.4 Risk Benefit Summary**

Subjects in this clinical study are healthy lactating volunteers who choose to stop breastfeeding their infant for the duration of the Treatment and Washout Periods (13 days) and will not receive any health benefit from participating in this study. Both bempedoic acid and bempedoic acid/ezetimibe FCDP are approved by the FDA and EMA.

This study will provide evidence-based data to inform lactating women in the US with HeFH or ASCVD and their health care providers whether to continue with treatment of bempedoic acid or bempedoic acid/ezetimibe FCDP during breast feeding.

Please refer to the most recent **IB** for more detailed information regarding previous human experience along with the **USPIs** and the **SmPCs** for bempedoic acid and bempedoic acid/ezetimibe FCDP.

## 5. OBJECTIVES AND ENDPOINTS

### 5.1 Objectives

#### 5.1.1 Primary Objective

The primary objectives of this study are to estimate infant exposure to bempedoic acid or bempedoic acid and ezetimibe:

- estimate the daily infant dosage and the relative infant dose (RID) of bempedoic acid in mature breast milk after administration of bempedoic acid for 6 consecutive days, and
- estimate the daily infant dosage and RID of bempedoic acid and ezetimibe in mature breast milk after administration of bempedoic acid/ezetimibe FCDP for 6 consecutive days.

#### 5.1.2 Secondary Objectives

The secondary objectives of this study are to characterize the excretion of bempedoic acid or ezetimibe in mature breast milk of healthy lactating women who receive once daily dose of bempedoic acid or bempedoic acid/ezetimibe FCDP for 6 consecutive days:

- determine concentrations of bempedoic acid, active metabolite ESP15228 and bempedoic acid glucuronide in mature breast milk collected over 24 hours from healthy subjects administered bempedoic acid or bempedoic acid/ezetimibe FCDP, and
- determine concentrations of ezetimibe and metabolite ezetimibe-glucuronide in mature breast milk collected over 24 hours from healthy subjects administered bempedoic acid/ezetimibe FCDP.

#### 5.1.3 Safety Objective

The safety objective of this study is to evaluate the safety of 6 consecutive doses of bempedoic acid or bempedoic acid/ezetimibe FCDP in healthy lactating women.

### 5.2 Endpoints

#### 5.2.1 Pharmacokinetic Assessments

##### 5.2.1.1 Primary Endpoints

Bempedoic acid and ezetimibe assessments include:

- daily infant dosage calculated as the cumulative amount excreted in breast milk per day, and
- RID calculated as the ratio of total infant daily dose per kg body weight and maternal daily dose per kg of body weight multiplied by 100.

### **5.2.1.2 Secondary Endpoints**

Bempedoic acid, ezetimibe, and metabolites (ESP15228, bempedoic acid glucuronide, and ezetimibe-glucuronide) assessments include:

- amount excreted in each breast milk collection, calculated as the product of concentration and milk volume collected,
- area under the milk concentration-time curve (AUC) over the 24-hour collection interval,
- average milk concentration based on milk AUC,
- peak and trough milk concentrations and the time of peak milk concentrations, and
- plasma trough concentrations at 24 hours after the last dose on Day 6.

### **5.2.2 Safety Endpoints**

Adverse events (all and treatment-emergent), clinical laboratory parameters, vital signs, and physical examinations will be collected.

[figure not shown]
## 6. INVESTIGATIONAL PLAN

### 6.1 Overall Study Design

This is a Phase 4, open-label study that will estimate the daily infant dosage and RID for bempedoic acid and bempedoic acid/ezetimibe FCDP and characterize the excretion of bempedoic acid, ezetimibe, and metabolites ESP 15228, bempedoic acid glucuronide, and ezetimibe-glucuronide in the mature breast milk of healthy women. The study will enroll 16 healthy lactating subjects, who will be randomized in a 1:1 ratio to receive either bempedoic acid (Cohort 1) or bempedoic acid/ezetimibe FCDP (Cohort 2), who choose to stop breastfeeding their infant for the duration of the Treatment and Washout periods (13 days). After signing the informed consent form (ICF), subjects will enter the Screening Period for up to 42 days, followed by a 6-day Treatment Period and a 7-day Washout Period. At Visit T1, subjects will be administered IMP at the clinical research unit CRU. The IMP will then be self-administered at home on Day 2 through Day 5. Study staff will phone subjects Day 2 through Day 5 to ensure IMP is being taken appropriately and remind subjects to discard breast milk produced after the first dose of IMP. Subjects will check-in to the CRU on the evening of Day 5 (with Sponsor approval the subject may check-in to the CRU on the morning of Day 6) for Visit T2 and start a 24-hour breast milk collection after the last dose of IMP on the morning of Day 6. Serum PK samples will be obtained on Day 7, approximately 24 hours after IMP administration on Day 6. Subjects will be discharged from the CRU on the morning of Day 7 approximately 24 hours after Day 6 dosing and the completion of all Day 7 assessments. At the end of the Washout Period on Day 13, all subjects will be contacted by phone for a Post-treatment Follow-up Visit (Visit FU1). Once the call is complete, subjects may resume feeding their infants breast milk that is currently being produced. On Day 43 (Visit FU2), study staff will contact subjects by phone to assess for SAEs and if the patient was able to resume breastfeeding (if intended).

Please refer to [Appendix 1](#) for a detailed Schedule of Assessments.

**Figure 1: Study Schematic**

### 6.2 Scientific Rationale

Consistent with the FDA's Draft Guidance for Industry, Clinical Lactation Studies: Considerations for Study Design ([FDA May 2019](#)) this Phase 4 study is designed to characterize the excretion of bempedoic acid or bempedoic acid and ezetimibe in mature human breast milk.

The data generated from this study will aid in assessing exposure and potential effects on the breastfed infant.

### **6.3      Estimated Study Duration**

Each subject will be in the study for up to 55 days. The 55 days are inclusive of an up to 42 days Screening Period followed by a 6-day Treatment Period and a 7-day Washout Period.

### **6.4      Number of Centers**

Up to 2 clinical research units (CRU) will participate in this study in the US. Additional sites may be invited to participate to ensure study timelines are met.

### **6.5      Number of Subjects**

The study will enroll approximately 16 healthy lactating women randomized in a 1:1 ratio of bempedoic acid (Cohort 1) to bempedoic acid/ezetimibe FCDP (Cohort 2).

### **6.6      Subject Number and Identification**

A unique subject identification number will be assigned to each subject to identify each subject throughout the study. Subject identification numbers will be assigned sequentially by the study site at the time of informed consent at the Screening Visit (Visit S1).

### **6.7      Subject Withdrawal and Replacement**

A subject is free to withdraw from the study at any time. Approximately 16 (8 bempedoic acid [Cohort 1] and 8 bempedoic acid/ezetimibe FCDP [Cohort 2]) healthy lactating female subjects will be enrolled. If a subject discontinues the study early or does not receive 6 daily doses of IMP or does not complete the 24-hour breast milk collection after Day 6 dosing, a replacement subject will be enrolled and assigned to the same treatment. The site must notify the Sponsor of any early withdrawals.

### **6.8      End of Study**

A subject is considered to have completed the study if all phases of the study are completed including the Follow-up Visit (FU1) on Day 13.

The end of the study is defined as the date of the Follow-up Visit (FU1) on Day 13 for the last active subject in the study.

Study staff will contact subjects by phone 30 days (Day 43, FU2) after FU1 to assess for serious adverse events (SAEs) and if the patient was able to resume breastfeeding (if intended).

## 7. SELECTION OF SUBJECTS

### 7.1 Subject Inclusion Criteria

Each subject must meet the following criteria to be eligible for this study.

1. The subject must be willing to provide written informed consent before any study-specific procedures are performed.
2. The subject must be 18 to 45 years old, inclusive.
3. The subject must be a lactating female who had a normal full-term pregnancy and has been actively breastfeeding or pumping for at least 4 weeks; lactation must be well-established per Investigator discretion.
4. The subject must be willing to pump regularly during the study to maintain milk supply and discontinue breastfeeding for the entire 13-day Treatment and Washout Periods.
5. The subject must not be pregnant.
6. The subject must be surgically sterile by hysterectomy, bilateral oophorectomy, and/or tubal ligation, or willing to use 1 acceptable method of birth control unless they have agreed to follow the definition of abstinence. The minimal requirement of adequate contraception should be started on Day 1 and continued during the study period and for at least 30 days after the last dose of IMP. Acceptable methods of birth control include:
  - an intrauterine device (IUD) with or without hormones;
  - established use of oral, implanted, transdermal, injectable, or hormonal method of contraception associated with inhibition of ovulation;
  - barrier methods including condom or occlusive cap with spermicidal foam or spermicidal jelly;
  - vasectomized male partner who is the sole partner for this subject; or,
  - true abstinence (when this is in line with the preferred and usual lifestyle of the subject). Note: periodic abstinence (e.g., calendar, ovulation, symptothermal, post-ovulation methods), declaration of abstinence for the duration of the trial, and withdrawal are not acceptable methods of contraception.

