### **Diagnosis and Criteria for Inclusion:**

#### **Inclusion Criteria:**

Each subject must meet the following criteria to be eligible for this study.

1. The subject must be willing to provide written informed consent before any study-specific procedures are performed.
2. The subject must be 18 to 45 years old, inclusive.
3. The subject must be a lactating female who had a normal full-term pregnancy and has been actively breastfeeding or pumping for at least 4 weeks; lactation must be well-established per Investigator discretion.
4. The subject must be willing to pump regularly during the study to maintain milk supply and discontinue breastfeeding for the entire 13-day Treatment and Washout Periods.
5. The subject must not be pregnant.
6. The subject must be surgically sterile by hysterectomy, bilateral oophorectomy, and/or tubal ligation, or willing to use 1 acceptable method of birth control unless they have agreed to follow the definition of abstinence. The minimal requirement of adequate contraception should be started on Day 1 and continued during the study period and for at least 30 days after the last dose of IMP. Acceptable methods of birth control include:
  - an intrauterine device (IUD) with or without hormones;
  - established use of oral, implanted, transdermal, injectable, or hormonal method of contraception associated with inhibition of ovulation;
  - barrier methods including condom or occlusive cap with spermicidal foam or spermicidal jelly;
  - vasectomized male partner who is the sole partner for this subject; or
  - true abstinence (when this is in line with the preferred and usual lifestyle of the subject). Note: periodic abstinence (e.g., calendar, ovulation, symptothermal, or post-ovulation methods), declaration of abstinence for the duration of the trial, and withdrawal are not acceptable methods of contraception.

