### **8.4 Treatment Assignment, Randomization, and Blinding**

#### **8.4.1 Treatment Assignment**

Subjects will receive open-label IMP during the Treatment Period of the study. Subjects will be randomized (Visit T1) to receive either bempedoic acid (Cohort 1) or bempedoic acid/ezetimibe FCDP (Cohort 2). The IMP will be taken Day 1 through Day 6 of the treatment period.

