#### **10.3.1 Screening Week -6 (Visit S1; Day -42 through Day -1)**

The screening period will begin with a screening visit (Visit S1) that will occur up to 6 weeks prior to randomization (Visit T1). Visit S1 will allow the Investigator to assess the subject's eligibility. After the subject provides informed consent ([Section 10.1](#)), the subject will undergo the following assessments:

- demographics;
- medical history including gestational age of infant at delivery, date of delivery, stage of lactation, length of time post-partum, smoking and alcohol intake;
- Review of current breastfeeding practices per subject report, including:
  - frequency and duration of feeds for infants fed from the breast,
  - bottles/day and ounces/day for infant's fed pumped breast milk from a bottle, and
  - use of formula supplementation (bottles/day, ounces/day and duration of supplementation);
- confirm subject is maintaining adequate breast milk production (document duration of weaning, if applicable) per subject report;

- confirm infant is able to bottle feed prior to randomization (Visit T1) per subject report;
- confirm adequate breast milk/infant formula is available to feed the infant after first dose of IMP (Visit T1) through Day 13 (Visit FU1) per subject report;
- concomitant medication review;
- adverse event review;
- physical exam;
- weight, height, and BMI;
- vital signs;
- clinical lab evaluations (blood chemistry, hematology and serology);
- assessment of renal function (eGFR calculated according to MDRD formula);
- assessment for liver disease (according to Child Pugh Classification score);
- serum pregnancy test;
- urine drug and alcohol screen; and
- schedule optional lactation consultant visit.

Note: subjects must understand that they will not be able to feed their infant breast milk produced after the first dose of IMP through Day 13.

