**Table 2: Safety Laboratory Parameters**

Clinical Laboratory Tests	
Hematology: 
 
hematocrit (Hct)
 
hemoglobin (Hgb)
 
mean corpuscular hemoglobin (MCH)
 
mean corpuscular hemoglobin concentration (MCHC)
 
mean corpuscular volume (MCV)
 
platelet count
 
red blood cell (RBC) count
 
white blood cell (WBC) count with differentials
 
	Clinical Chemistry: 
 
albumin (Alb)
 
alkaline phosphatase (ALP)
 
alanine aminotransferase (ALT; SGPT)
 
aspartate aminotransferase (AST; SGOT)
 
blood urea nitrogen (BUN)
 
calcium (Ca)
 
carbon dioxide (CO2)
 
chloride (Cl)
 
creatinine
 
creatine kinase (CK)
 
glucose
 
lactate dehydrogenase (LDH)
 
phosphorus
 
potassium (K)
 
sodium (Na)
 
total bilirubin (TB) and direct bilirubin
 
total protein
 
uric acid
 

Serology: 
 
hepatitis B surface antigen (HBsAg)
 
hepatitis C virus antibody (HCV-Ab)
 
HIV antigen/antibody
 
	
Pregnancy Testing: 
 
serum pregnancy (Visit S1 only)
 
urine pregnancy (Visits T1 and T2 [Day 7] only)
 
	Coagulation Parameters (to assess Child Pugh Classification of Liver Disease at screening): 
 
prothrombin time
 
international normalized ratio (INR)
 

Urine drug and alcohol screen: 
 
alcohol
 
amphetamines
 
barbiturates
 
benzodiazepines
 
cocaine (metabolite)
 
methadone
 
phencyclidine
 
 opiates
 
tetrahydrocannabinol (THC)/cannabinoids
 
	

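### Contraception is required only from Day 1, so a woman who first starts a barrier method or IUD that day could carry a conception too recent for the Day 1 urine test through all six doses

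*Protocol*

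**What the plan says.** Criterion 6 in Protocol Section 7.1 asks that a woman who is not surgically sterile be willing to use one acceptable method. On timing it says: "The minimal requirement of adequate contraception should be started on Day 1 and continued during the study period and for at least 30 days", counted from the final dose. The Synopsis has the same start: "The minimal requirement of adequate contraception should be started on Day 1".

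The acceptable methods differ in what they imply about the days before Day 1:

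- Hormonal: "established use of oral, implanted, transdermal, injectable, or hormonal method of contraception associated with inhibition of ovulation". A new start on Day 1 does not qualify.
- IUD: "an intrauterine device (IUD) with or without hormones". No prior use is required.
- Barrier: "barrier methods including condom or occlusive cap with spermicidal foam or spermicidal jelly". No prior use is required.
- A vasectomized sole partner, or abstinence that is the woman's usual lifestyle. Both normally protect before Day 1 as well.

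Pregnancy is tested three times. A serum test is done at the screening visit only, a visit "that will occur up to 6 weeks prior to randomization (Visit T1"). The other tests are "urine pregnancy (Visits T1 and T2 [Day 7] only"). Dosing is stated in Section 8.4.1: "The IMP will be taken Day 1 through Day 6 of the treatment period". Section 10.3.4.3 places the Day 7 test after the 24-hour milk collection that follows the sixth dose.

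**The concern.** The protocol treats exposure in pregnancy as something to avoid. Criterion 5 excludes pregnant women, criterion 6 extends contraception to 30 days after the last dose, and Section 13.2.6 stops the drug at once if a subject becomes pregnant and follows the pregnancy to its outcome. Yet the days just before the first dose have no required contraception, and the most recent of them are the ones a pregnancy test on Day 1 cannot check. By the next scheduled test there is no dose left to stop.

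Participants are healthy volunteers who, under Section 4.4, gain no health benefit. An avoidable gap in their protection therefore needs a reason, and the protocol gives none. What is at stake is participant and fetal safety, not the analysis.

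**Working it through.** The plan states no figure to reproduce, so the check is date arithmetic on the visit schedule.

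**Inputs from the documents**
- Required contraception starts on Day 1 (Section 7.1, criterion 6).
- Urine tests are on Day 1 and Day 7, and the serum test is at S1 only, between Day -42 and Day -1 (Table 2; Section 10.3.1).
- Doses are on Days 1 to 6 (Section 8.4.1), each 180 mg bempedoic acid, plus 10 mg ezetimibe in Cohort 2 (Table 1).
- There is no Day 0: the day before the first dose is Day -1 (SAP Section 7.2).

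**Assumption, not in the documents**
- L is the number of days from conception to a positive urine test, taken as 7 to 14. Intercourse and conception are treated as the same day; any interval between them adds to L.

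**Steps**
1. A conception on Day -d is d days old at the Day 1 test. It is missed if d < L, so the missed days before Day 1 are d = 1 to L - 1, which is L - 1 days.
2. No test is scheduled on Days 2 to 6. At the Day 7 test the same conception is d + 6 days old. It is missed again if d + 6 < L, that is for d = 1 to L - 7.
3. If Days -14 to -1 were covered, the remaining uncovered days would be d = 15 to L - 1, which is max(0, L - 15) days.

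| Assumed L | Uncovered now (L - 1) | Of these, also missed on Day 7 (L - 7) | Uncovered with a 14-day run-in |
|---|---|---|---|
| 7 | 6 (Day -6 to -1) | 0 | 0 |
| 10 | 9 (Day -9 to -1) | 3 (Day -3 to -1) | 0 |
| 14 | 13 (Day -13 to -1) | 7 (Day -7 to -1) | 0 |
| 17 (beyond the assumed range) | 16 (Day -16 to -1) | 10 (Day -10 to -1) | 2 |

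A woman in this window would take all six doses before the next test: 6 x 180 = 1,080 mg bempedoic acid and, in Cohort 2, 6 x 10 = 60 mg ezetimibe. After Day 7 no further pregnancy test is scheduled; the Day 13 and Day 43 contacts are by phone.

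**Who is in the window.** Women who are surgically sterile, already using an IUD or barrier, on established hormonal contraception, with a vasectomized sole partner, or habitually abstinent are outside it. What remains is a woman with recent unprotected intercourse who first uses a barrier method or has an IUD placed on Day 1. The documents do not allow that number to be computed.

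**The case against.** The strongest case against acting is that no consequence has been shown. The group is narrow, the study enrols about 16 women, and the cumulative doses are simply six labelled doses that say nothing about risk so early in pregnancy. Risk information is referred to the Investigator's Brochure and product labels, so a Day 1 start may have been a reasoned choice. Criterion 6 also calls its requirement minimal, so a site may ask for more. The screening serum test can fall as late as Day -1, and Section 10.3.2 requires all eligibility criteria to be met again on Day 1.

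Most of this stands as a limit on size. It does not close the gap. A site that follows the criterion exactly may enrol a woman who starts a barrier method on Day 1. Nothing requires screening to be close to Day 1, and a serum test on Day -1 would have a lag of its own, also not stated. Rechecking eligibility on Day 1 relies on the same urine test.

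A reader might infer that the documents establish a gap of 6 to 13 days. They do not: that range is the assumed lag of 7 to 14 days less one. Nor does it mean only days 6 to 13 before dosing. The window always ends on Day -1, and the assumption fixes only where it begins.

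**Conclusion.** The gap is real, narrow and cheap to close. For women who first start a barrier method or IUD on Day 1, a conception within the urine test's detection lag before Day 1 is not guarded against and cannot be found by a scheduled test before dosing ends. This holds for any lag longer than one day. The length of the window, 6 to 13 days, rests wholly on the assumed lag of 7 to 14 days.

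A reader might go further and infer a quantified fetal risk, a probability of exposure, or a weakness in the infant-dose results. The documents support none of these. They give no fetal-risk figure and no count of women without a method in place, and daily infant dosage and RID do not depend on criterion 6. The case rests on the protocol's own aim of avoiding exposure in pregnancy. It justifies a wording change on safety grounds and nothing larger.

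**What to change.** In criterion 6 (Section 7.1 and Synopsis), replace the Day 1 start clause with: *must have used an acceptable method, or had no unprotected intercourse, for at least 14 days before Day 1*. Keep the requirement to use an acceptable method, or true abstinence as the criterion defines it, from Day 1 through at least 30 days after the last dose. Update the consent text to match. The test schedule and the rule for stopping drug stay as they are.

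Allowing no unprotected intercourse as an alternative matters. The criterion's own definition rejects abstinence that is not habitual, so without this alternative a woman who uses no method but has no recent risk would be delayed for nothing.

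The cost is one clause in two places plus the consent form, with no added visits or tests. A woman with recent unprotected intercourse waits up to 14 days, within the 42-day screening window; others wait no longer than now. The 14 days cover any lag up to 15 days. A longer lag would leave a small residual gap, for example 2 days at a lag of 17.
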